#### **36) Per Protocol (PP) Population**

The PP population is defined as any subject in the ITT who do not have any major protocol deviations and in whom the Pure-Vu system was utilized as planned. This population will also be used for all efficacy analyses.

#### **37) Inadequate Bowel Preparation (IBP) Population**

The IBP population is defined as any subject that were identified to have inadequate prep after initial OC and were indicated for cleansing with the Pure-Vu System and did not have any major protocol deviations.

#### **38) Primary Endpoint Analysis**

The primary endpoint is conversion rate of inadequate colonoscopies to adequate colonoscopies after the use of the Pure-Vu EVS System, where inadequate OCs defined as such if any of the following are met:

- BBPS < 6 (Adequacy is defined as BBPS of 2 or greater in each segment)
- Inability to identify >5mm polyps

Document Title: Colonoscopy: Demonstrating Effective Salvage of Inadequate Colonoscopies Utilizing the Pure-Vu EVS System	Outpatient	Document No. CL00052	Amendment 2.0	Page 31 of 46
---	------------	--------------------------------	-------------------------	---------------

The conversion rate,  $\theta$ , is defined as number of preps inadequate with SOC and adequate after Pure-VU EVS System divided by the number of preps inadequate with SOC.

$$H_0: \theta \leq 0.30$$

$$H_1: \theta > 0.30$$

The conversion rate and its two-sided 95% exact binomial interval will be presented and compared to the 30% performance goal. The proportion of preps inadequate after SOC and inadequate after SOC + Pure-Vu will also be reported.

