## 1) Protocol Synopsis

Study Summary	
Study Purpose	
The aim of this study is to demonstrate that the use of the Pure-Vu EVS System can salvage inadequately prepared optical colonoscopies (OCs) to adequate OCs.
 
Inadequate OCs defined as such if any of the following are met:
 

▪ Boston Bowel Preparation Score (BBPS) < 6 (Adequacy is defined as BBPS of 2 or greater in each segment)

▪ Inability to identify > 5mm polyps

Primary Objective	The primary objective of this study is to demonstrate the reduction of inadequate colonoscopies when Pure-Vu EVS System is used to salvage inadequately prepped colons as defined by the multi-society guidelines (USMSTF).
Secondary Objective	The secondary objective of this study is to assess the impact of the Pure-Vu System on patient outcomes.
Study Procedures	
Protocol Number	CL00052
Protocol Title	Outpatient Colonoscopy: Demonstrating Effective Salvage of Inadequate Colonoscopies Utilizing the Pure-Vu EVS System
Study Sponsor	Motus GI Medical Technologies LTD. [name]

Document Title: Colonoscopy: Demonstrating Effective Salvage of Inadequate Colonoscopies Utilizing the Pure-Vu EVS System	Outpatient	Document No. CL00052	Amendment 2.0	Page 8 of 46
---	------------	--------------------------------	-------------------------	--------------

	[name]
Study Type	Multicenter, Prospective, Consecutive Series, Pragmatic Clinical Trial
Study Device	Pure-Vu EVS System
Study Phase	Post-market
510 (k) Number	K220007 Class II
Study Location	United States
Study Duration	Study period will last approximately 12 months
Planned Follow-Up	Follow-up call will be conducted within 14 business days after the procedure
Subject Population	Patients who are eligible and are scheduled for an outpatient colonoscopy procedure

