Pure-Vu System: Generation 1  Clinical Study: Outpatient study including 50 outpatients in 2 sites in Israel and Spain (10)	Study subjects indicated for screening, diagnostic or surveillance indication were enrolled and received minimal pre-procedure bowel preparation  To ensure an inadequately prepped colon, subjects underwent a reduced preparation consisting of dietary restrictions (no dried fruit, seeds or nuts) starting 2 days prior to the colonoscopy, and 18 to 24 hour clear liquid diet with a split dose of 20mg Bisacodyl. The cleansing quality was evaluated using BBPS before and after use of the Pure-Vu System.	Study reported a cecum intubation rate of 98%. Pure-Vu increased BBPS scores and increased the proportion of patients with an adequate cleansing level (31% of patients at baseline vs. 98% post Pure-Vu cleansing) and mean BBPS improvement of 5 to 9.
Pure-Vu System: Generation 1  Clinical Study: Inpatient Study including 95 hospitalized subjects from 6 clinical sites in the US and Germany (11)	This inpatient study included 95 hospitalized patients. One patient was excluded due to the discovery of ulcerative colitis during the procedure which was a study exclusion. A total of 94 subjects (60% male) were enrolled from 6 clinical study sites. The mean age of the subjects was $62.44 \pm 13.47$ (range 28-88y) and the mean	The proportion of patients with an adequate cleansing level ( $BBPS \geq 2$ in each of the evaluated colon segments), increased significantly from 38% (32/84) at baseline to 96% (81/84) after use of Pure-Vu ( $P < 0.001$ ). Increase of adequate preparation, defined as pre Pure-Vu BBPS scores of 2 or higher, was reported in 60%, 62%, and 47% to 100%, 99%, and 97% of the left-side,

Document Title: Colonoscopy: Demonstrating Effective Salvage of Inadequate Colonoscopies Utilizing the Pure-Vu EVS System	Outpatient	Document No. CL00052	Amendment 2.0	Page 19 of 46
---	------------	--------------------------------	-------------------------	---------------

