## **29) Colonoscopy Procedure**

The insertion during the colonoscopy procedure will be performed by the clinical study investigator(s), experienced in GI endoscopy according to the local standard of care. The type of

Document Title: Colonoscopy: Demonstrating Effective Salvage of Inadequate Colonoscopies Utilizing the Pure-Vu EVS System	Outpatient	Document No. CL00052	Amendment 2.0	Page 28 of 46
---	------------	--------------------------------	-------------------------	---------------

sedation will not be dictated by the study but will be documented. The colonoscope will be prepared and the procedure will proceed per the standard of care.

During the procedure, the study endoscopist will be requested to document BBPS for each colon segment. Once the endoscopist notices an inadequate segment, the endoscopist should attempt to cleanse per his/her standard of care practices with the goal to achieve a BBPS of 2 or higher for that segment. This should be repeated for each colonic segment. If the study definition of inadequate is met in any segment, even after SOC cleansing, the endoscopist is required to take pictures of all accessed segment(s) including the inadequate segment(s). The endoscopist will withdraw the colonoscope and all procedural outcomes and findings should be documented. Then the Pure-Vu Oversleeve will be placed onto the colonoscope, and the procedure will be performed utilizing the Pure-Vu System for cleansing. Photo-documentation of each segment will be required to show BBPS after Pure-Vu use. Once the procedure has been completed with Pure-Vu, procedural outcomes (inclusive of final adequacy determination after Pure-Vu use and findings will be documented again.

If during the standard of care colonoscopy, the patient cannot proceed onto Pure-Vu and/or will be deemed an incomplete colonoscopy due to any reason other than inadequate prep, that subject will be withdrawn from the study. Such an instance might occur when a mass or stricture is found, or when an active inflammatory condition is detected but is it ultimately up to the Principal or Sub-Investigator to make the determination during the procedure.

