### **31) Statistical Analysis**

### **32) Sample Size Determination**

The study is planned to enroll at fifteen sites and will enroll until 115 subjects are identified with inadequate bowel prep.

Assuming a 12% inadequate prep rate 1067 patients would be enrolled to achieve 115 patients inadequate bowel preparation. The final sample size, however, will be determined by the number needed to undergo colonoscopy to achieve 115 and therefore may be greater than or less than 1067.

The sample size of 115 was determined to provide at least 90% power for the primary endpoint of demonstrating conversation rate of inadequate colonoscopies after the use of the Pure-Vu EVS System is greater than a 30% performance goal.

Assuming a true conversion rate of 50%, then 115 inadequately prepped patients undergoing Pure-Vu with the opportunity to convert to adequate prep will provide  $\geq 99\%$  power and at least 115 patients for safety. To be conservative, 115 inadequately prepped patients will provide  $\geq 90\%$  power to produce an exact 95% CI  $> 30\%$  even if the true conversion rate is 45%.

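### The primary endpoint defines inadequate by total BBPS but adequate by segment, so on the BBPS criterion colons scored 3/3/0, 3/2/1 or 3/3/1 are neither

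*Protocol*

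**What the plan says.** Section 38 calls a colonoscopy inadequate if either of two criteria is met. The first is "BBPS < 6 (Adequacy is defined as BBPS of 2 or greater in each segment"). The second is that polyps larger than 5 mm cannot be identified. The same pair appears in the synopsis (study purpose and primary endpoints) and in sections 13 and 16, each time with the parenthesis "Adequacy is defined as BBPS of 2 or greater in each segment".

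The conversion rate in section 38 is the "number of preps inadequate with SOC and adequate after Pure-VU EVS System divided by the number of preps inadequate with SOC". Its exact 95% interval is compared with 30%. Section 32 "will enroll until 115 subjects are identified with inadequate bowel prep". Section 37 puts in the IBP population those "identified to have inadequate prep after initial OC and were indicated for cleansing with the Pure-Vu System".

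Section 29 works by segment. SOC cleansing is done "with the goal to achieve a BBPS of 2 or higher for that segment", and the step to Pure-Vu begins "If the study definition of inadequate is met in any segment, even after SOC cleansing".

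**The concern.** The bullet contains two rules on different scales. The rule for inadequate uses a total, and the rule for adequate uses the worst segment. A colon can fail both. After SOC, such a colon is not inadequate under the listed BBPS criterion, so read literally it is outside the denominator and the 115-case count. Section 29's wording would nevertheless send it to Pure-Vu. Whether it then belongs to the IBP population depends on which section is followed.

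After Pure-Vu, the stated adequacy definition makes the same colon a failure, which largely settles the numerator. But the listed criterion does not call it inadequate either, so it would also be missing from the proportion that section 38 reports as inadequate after SOC plus Pure-Vu.

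This definition fixes the denominator, the stopping count and the numerator of the trial's only hypothesis test.

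**Working it through.** **Inputs.** Segment scores run from 0 to 3 (Appendix B). There are three segments: left, transverse and right (the inpatient study in section 9). Inadequate means total < 6; adequate means every segment ≥ 2 (section 38). There are 115 cases, the goal is 30%, the interval is exact two-sided 95%, and the assumed true rates are 50% and 45% (sections 32 and 38). The inadequate rate is 12% and attrition 10% (synopsis).

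**1. The plan's own figures reproduce.** The smallest count out of 115 whose Clopper-Pearson lower bound exceeds 30% is 45:
- 45/115 = 39.1%, lower bound 30.2%
- 44/115 = 38.3%, lower bound 29.4%

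Power is P(X ≥ 45) with X binomial(115, p): 99.3% at p = 0.50 and 91.3% at p = 0.45. Enrollment: 115/0.9 rounds up to 128, and 128/0.12 = 1,066.7, so 1,067. None of this depends on the BBPS wording.

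**2. The gap.** Three segments with four possible scores give 4³ = 64 ordered patterns.

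| Rule | Patterns |
|---|---|
| Total < 6 (inadequate) | 44 |
| Every segment ≥ 2 (adequate) | 8 |
| Both | 0 |
| Neither | 64 − 44 − 8 = 12 |

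The 12 are the 3 orderings of 3/3/0 (total 6), the 6 of 3/2/1 (total 6) and the 3 of 3/3/1 (total 7). These are counts of score patterns, not shares of patients. With the rule of any segment below 2, the split is 44 + 12 = 56 inadequate and 8 adequate, with nothing left over.

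**3. Effect on the test if a total of 6 or more were read as adequate after Pure-Vu.** One case moves the rate by 1/115 = 0.87 points. Success needs 45, so the verdict reverses when the count falls to 44:
- from 52/115 (45%): 52 − 44 = 8 cases
- from 57/115 (50%): 57 − 44 = 13 cases

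Near the threshold fewer are needed. With assumed counts of 40 colons adequate in every segment and 5 in the gap, the segment rule gives 40/115 = 34.8% (lower bound 26.1%, fails). Counting the 5 as adequate gives 45/115 = 39.1% (lower bound 30.2%, passes).

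**4. How common the gap might be after Pure-Vu.** In the inpatient study in section 9 (Generation 1 device), adequacy by segment "increased significantly from 38% (32/84) at baseline to 96% (81/84) after use of Pure-Vu". That leaves 84 − 32 = 52 inadequate at baseline and 84 − 81 = 3 not adequate afterwards. If no baseline-adequate colon worsened (an assumption), at most 3/52 = 5.8% ended in the gap, with an exact 95% interval of 1.2% to 15.9%. This is a ceiling, because all three would have to show a gap pattern.

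**5. How common it might be after SOC.** The protocol gives nothing from which to estimate this, so the effect on the denominator cannot be sized.

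**The case against.** The best defence is that the intent is clear. The parenthesis expressly defines adequacy wherever the threshold appears, section 29 works by segment, and the inpatient study in section 9 used the same segment rule. On that reading the threshold of 6 is loose shorthand for failing it. The synopsis and section 37 also tie the 115 cases and the IBP population to treatment with, or indication for, Pure-Vu, so a 3/3/1 colon sent to Pure-Vu under section 29 would ordinarily be counted. The polyp criterion would plausibly catch 3/3/0, since Appendix B describes a score of 0 as mucosa not seen, and it may catch some segments scored 1. Finally, no section calls these colons adequate, so the reclassification counts rest on a reading that the text does not state.

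Much of this stands: the segment rule is probably what was meant, the numerator is largely settled, and the effect is probably small. It does not close the gap. The parenthesis defines adequate and leaves the criterion for inadequate as a total, and that criterion governs the denominator. Section 29 refers back to the study definition, and a total cannot be met within one segment. The polyp criterion is a separate judgement by the endoscopist that makes no reference to the score.

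**Conclusion.** The concern holds. On the BBPS criterion the endpoint definition leaves exactly three score patterns unclassified, and the same colon can be in or out of the primary analysis depending on the section followed. This is a stated rule that conflicts with itself, not detail left for the SAP.

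The consequence is probably modest. At observed rates of 45% to 50%, between 8 and 13 of 115 cases would have to change class to reverse the verdict, and then only if a total of 6 or more were taken as adequate. The smaller figure, 8/115 = 7.0%, lies above the 5.8% ceiling from the inpatient study but within its upper limit of 15.9%. That ceiling assumes that no adequate colon worsened and comes from an earlier device generation in inpatients. The effect through the denominator is unknown in size and direction. The planned 115 cases and their power calculation are unaffected. It should be fixed because it sits in the only hypothesis test and costs little to remove.

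**What to change.** For endpoint classification, use one BBPS rule that is the exact complement of the protocol's own adequacy definition: not adequate if any segment scores below 2. Keep the existing polyp criterion beside it. State the rule in identical words in the synopsis and sections 13, 16 and 38. Apply it after SOC, for the denominator and the accrual count, and again after Pure-Vu, for the numerator. Report total BBPS descriptively. Reconcile the wording of section 29 with the endpoint definition; the clinical trigger for Pure-Vu remains the sponsor's decision.

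The cost is a wording change in several sections. Section 29 already asks for a score in each segment, so no new data are needed. The reported conversion rate may be slightly lower than if a total of 6 or more counted as adequate after Pure-Vu. Colons added to the denominator could move it either way.

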### **39) Secondary Endpoint Analysis**

All secondary endpoints will be summarized using descriptive statistics and full details on additional planned analyses will be provided in the prospective Statistical Analysis Plan.

### **40) Tertiary Endpoint Analysis**

All tertiary endpoints will be summarized using descriptive statistics and full details on additional planned analyses will be provided in the prospective Statistical Analysis Plan.

### **41) Safety Endpoint Analysis**

All adverse events (AE) and serious adverse events (SAE) that are definitely and/or potentially attributed to Pure-Vu will be summarized using descriptive statistics.

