Sample Size	
Subjects will be enrolled until 115 inadequate bowel prep cases via SOC are accrued and subsequently treated with Pure-Vu. 115 IBP cases provides 90% power and with an expected 12% inadequate bowel prep rate and accounting for 10% attrition, approximately 1,067 subjects will need to be enrolled to achieve 115 inadequate preps required Pure-Vu. A minimum of 50% of enrollees with inadequate bowel prep must utilize Medicare or Medicaid as their insurance provider.
 
The following assumptions were considered for sample size calculation:
 

• Performance goal for 30% reduction

• <math>\geq 90\%</math> Power and two-sided <math>\alpha = 0.05</math>

• True reduction in IBP vs. SOC = 50%

• <math>\sim 10\%</math> attrition rate

Planned # of Sites	Up to 15 clinical sites

Document Title: Colonoscopy: Demonstrating Effective Salvage of Inadequate Colonoscopies Utilizing the Pure-Vu EVS System	Outpatient	Document No. CL00052	Amendment 2.0	Page 9 of 46
---	------------	--------------------------------	-------------------------	--------------

Primary Endpoints	
Rate of incomplete colonoscopies due to inadequate preparation salvaged to adequate colonoscopies with the use of the Pure-Vu EVS System.
 
Inadequate OCs defined as such if any of the following are met:
 

▪ BBPS < 6 (Adequacy is defined as BBPS of 2 or greater in each segment)

▪ Inability to identify > 5mm polyps

 
The estimated rate of salvaged preparations will be calculated and presented with exact two-sided 95% confidence interval: Number of preps inadequate with SOC and adequate after Pure-VU EVS System / Number of preps inadequate with SOC.
 
The lower bound will be compared to a 30% performance goal.

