## 19) Primary Safety Endpoint

A comparison of SAE rates between Pure-Vu subjects and the published serious complication rate of standard colonoscopy procedures (2.8%).

[figure not shown]
Document Title: Colonoscopy: Demonstrating Effective Salvage of Inadequate Colonoscopies Utilizing the Pure-Vu EVS System	Outpatient	Document No. CL00052	Amendment 2.0	Page 23 of 46
---	------------	--------------------------------	-------------------------	---------------

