## 21) Selection and Enrollment

A patient may be introduced to the study at the GI office when an outpatient colonoscopy is indicated. Once it's determined that the patient is interested in participation and eligible for participation, he or

Document Title: Colonoscopy: Demonstrating Effective Salvage of Inadequate Colonoscopies Utilizing the Pure-Vu EVS System	Outpatient	Document No. CL00052	Amendment 2.0	Page 25 of 46
---	------------	--------------------------------	-------------------------	---------------

she will be consented for the study. After conducting the consent process, obtaining informed consent, and answering questions, the subject will sign the sites' designated IRB approved informed consent form (ICF). This study also allows for an electronic consenting process. Enrollment of approximately 1,067 subjects is planned to achieve 115 patients with inadequate bowel prep.

Subjects' enrollment in the study will begin on the day of procedure and will last approximately 15 days, including the procedure day, and one follow up call during the follow up period (within 14 days after the procedure). Safety assessments will begin at the time of enrollment.

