#### **34) Safety Population**

The safety population is defined as any subject presented for procedure and enrolled into the study. This population will be used for all safety analyses.

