## 54) Adverse Event Recording and Reporting

Assessment of the occurrence of an AE will be based on changes in the subject's signs and symptoms. AEs will be monitored until a subject completes the study unless the Investigator

Document Title: Colonoscopy: Demonstrating Effective Salvage of Inadequate Colonoscopies Utilizing the Pure-Vu EVS System	Outpatient	Document No. CL00052	Amendment 2.0	Page 35 of 46
---	------------	--------------------------------	-------------------------	---------------

determines the event is related to the investigational device, in which case they will be monitored until resolution if possible. Medical care will be provided, as defined in the informed consent, for any AE related to study participation. AEs will be collected on an AE eCRF and applicable source documentation.

The following should not be considered an AE:

- A condition requiring a preplanned procedure unless the condition worsened since screening
- A preexisting condition found as a result of screening, unless the condition has worsened since enrollment.

All relevant AEs observed during this study, regardless of severity or relationship to the study device will be recorded on the appropriate eCRF. All relevant AEs are associated complications expected during colonoscopies, use of the Pure-Vu System, bowel preparation or anesthesia. It will be the responsibility of the reporting PI to determine if the AE is relevant.

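### Section 41 limits the safety summary to events attributed to Pure-Vu, which does not match the protocol's primary safety endpoint or safety population and names no summary for the roughly 940 standard-of-care-only subjects

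*Protocol*

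**What the plan says.** Section 41 (Safety Endpoint Analysis) is one sentence: AEs and SAEs "that are definitely and/or potentially attributed to Pure-Vu will be summarized using descriptive statistics". It gives no method for any comparison. Sections 39 and 40 refer further detail to the SAP; section 41 does not.

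Other sections are wider:

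- Section 19 gives the primary safety endpoint as "A comparison of SAE rates between Pure-Vu subjects and the published serious complication rate of standard colonoscopy procedures", with that rate put at 2.8%. It has no attribution limit.
- Section 44 defines an SAE irrespective of cause or relationship to the device.
- Section 34 defines the safety population as "any subject presented for procedure and enrolled into the study" and assigns it to all safety analyses.
- Section 54 says that relevant AEs "regardless of severity or relationship to the study device will be recorded on the appropriate eCRF".
- Section 30 and Appendix A give every subject the same follow-up call.
- In the synopsis, the attribution wording belongs to the secondary safety endpoint, and there it covers adverse events generally.
- Section 33 sets a general default, unless otherwise specified, of descriptive statistics by prep adequacy group and overall.

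**The concern.** Section 41 carries the attribution filter of the secondary safety endpoint, extends it explicitly to SAEs, and is the only safety analysis text in the protocol. The primary safety endpoint therefore has no matching analysis: an SAE in a Pure-Vu subject that the investigator judges unrelated counts under sections 19 and 44 but not under section 41. Attribution is a judgement made by unblinded investigators in a single-arm device study, so filtering on it can lower the reported rate. A filtered rate set against a published rate of serious complications would also not be like for like.

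The second consequence concerns subjects who never receive the device. They cannot have an event attributed to it, so section 41 reports nothing for most of the safety population. Yet their events are recorded under the same SAE definition, at the same sites and with the same call. They are the only source within the trial for the SAE rate that this ascertainment yields after standard colonoscopy. Without it, the Pure-Vu rate is read only against one external figure.

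**Working it through.** **1. Planned enrolment, reproduced.** Inputs: 115 inadequate preps ("The study is planned to enroll at fifteen sites and will enroll until 115 subjects are identified with inadequate bowel prep"), a 12% inadequate-prep rate (section 32) and 10% attrition (synopsis: "accounting for 10% attrition, approximately 1,067 subjects will need to be enrolled to achieve 115 inadequate preps required Pure-Vu").

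- 115 / 0.12 = 958.3, rounded up to 959
- 959 / (1 − 0.10) = 1,065.6, rounded up to 1,066

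The protocol states 1,067, so its figure reproduces to within one subject.

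**2. Size of the SOC-only group.**

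- By rate: 0.88 × 1,067 = 939
- By subtraction: 1,067 − 115 = 952
- After 10% attrition: 0.90 × 1,067 − 115 = 845

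So about 940 are enrolled and about 845 remain after attrition.

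**3. What the 2.8% comparison can show with 115 Pure-Vu subjects.** Exact (Clopper-Pearson) two-sided 95% intervals; with 0 events the upper limit is 1 − 0.025^(1/115) = 3.16%.

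| SAEs / 115 | Rate | Exact 95% CI |
|---|---|---|
| 0 | 0.0% | 0 to 3.2% |
| 3 | 2.6% | 0.5 to 7.4% |
| 7 | 6.1% | 2.5 to 12.1% |
| 8 | 7.0% | 3.05 to 13.2% |

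At a true rate of 2.8%, 115 × 0.028 = 3.2 SAEs are expected. No result puts the upper limit below 2.8%. The lower limit first exceeds 2.8% at 8 SAEs, an observed rate 7.0 / 2.8 = 2.5 times the benchmark. If the true rate were double the benchmark (5.6%), the chance of 8 or more SAEs is 32%.

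**4. What an SOC-only summary would add.** Assume, for illustration only, 2.8% in both groups. Expected SOC-only SAEs are 845 × 0.028 = 24 to 952 × 0.028 = 27. With 26/939 the SOC-only rate would be known to within 1.8 to 4.0%. The half-width of the interval for the difference is

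1.96 × √[0.028 × 0.972 × (1/115 + 1/939)] = 3.2 percentage points

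(also 3.2 with 845). Power at two-sided 5% (normal approximation), for 845 to 939 SOC-only subjects:

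| Assumed SOC-only rate | Doubling | Tripling |
|---|---|---|
| 2.8% | 39–40% | 78–79% |
| 1% | 22% | 46–47% |

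**5. Illustration with assumed counts.** 3/115 = 2.6% lies just under 2.8%. Against an assumed 9/939 = 1.0% (0.4 to 1.8%), the difference is +1.65 points (Newcombe 95% CI −0.3 to +6.5; Fisher p = 0.13). The table would show the reader a point estimate 2.7 times the in-trial rate (2.61 / 0.96), but it would not establish an excess.

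**The case against.** The strongest reply is that section 41 is not the whole safety analysis. Its wording closely follows the secondary safety endpoint in the synopsis, the primary endpoint is stated separately in section 19, and the layout of safety tables is commonly left to the SAP, which is not at hand. A published benchmark is also a legitimate choice for a post-market, single-arm study built on a performance goal. Much of this stands: using 2.8% is not an error, and not every table must appear in the protocol. It does not rescue section 41, which states a restriction rather than staying silent, does not defer to the SAP, and conflicts with sections 19, 34 and 44.

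A reader might infer that the SOC-only safety data will never be used or will enter no table. The documents do not support that. Section 34 assigns the all-enrolled population to all safety analyses, and the section 33 default would give descriptive statistics by prep adequacy group, which is close to the Pure-Vu versus SOC-only split. What can be said is that no safety summary or comparison for SOC-only subjects is named, and that the safety-specific section excludes their events.

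A reader might also infer that an internal comparison would show whether the added Pure-Vu pass carries more SAEs. It would not. Pure-Vu subjects are selected for inadequate preparation, which section 4 links to older age, opioid use, diabetes and obesity, and under section 29 they have the scope withdrawn and reinserted. Device, second insertion and patient mix cannot be separated, and about three expected Pure-Vu SAEs leave little power. Ascertainment is similar rather than identical: section 54 lets the investigator decide which AEs are relevant and monitors device-related events for longer.

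**Conclusion.** The point holds as an internal conflict with a cheap remedy. Section 41 filters on attribution; sections 19 and 44 define the primary safety endpoint without a filter, and section 34 covers all enrolled subjects. As written, the primary safety endpoint has no matching analysis, and no summary is named for about 940 enrolled SOC-only subjects (about 845 after attrition). The sole named comparator is weak at this size: 0/115 is still compatible with rates up to 3.2%, and an excess over 2.8% is shown only from 8/115 (7.0%).

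The group sizes rest on the protocol's 12% and 10% assumptions; the SOC-only event rates used above (2.8% and 1%) are mine. The conclusion does not depend on those rates. It does not extend to a claim that the data will go unused, or that the SOC-only group would give an unconfounded estimate of device risk.

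**What to change.** Amend section 41 to:

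1. Tabulate all AEs and SAEs regardless of attribution, separately for Pure-Vu and SOC-only subjects, over the same window, with exact 95% intervals for each group and an interval for the difference in SAE rate.
2. Keep Pure-Vu-attributed events as a subset of that table, serving the secondary safety endpoint.
3. State that the 2.8% comparison uses the all-cause SAE rate in Pure-Vu subjects, shown with its exact interval.
4. Label the between-group contrast descriptive, confounded by patient mix and the second insertion, and of low power.

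Subgroup breakdowns of this table should not be required: with about three expected Pure-Vu SAEs they would be nearly empty.

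The cost is a few sentences and one extra table from data already collected. The downside is a non-randomised contrast that could be over-read, hence the label.
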